3.5. Expanded-Enrollment Phase

3.5.1. 12- to <18-Month Age Stratum

The IRC will review all post–Vaccination 1, 7-day e-diary and AE data obtained from sentinel subjects aged 12 to <15 months. Based on the review, the IRC will select the bivalent rLP2086 dose level to be studied in the Stage 1 expanded-enrollment phase. Younger-age sentinel subjects cannot participate in the 120-µg dose level before the safety data of the 120-µg dose level have been found to be acceptable in the 120-µg older-age sentinel cohort.

The expanded-enrollment phase for this age group will enroll approximately 132 subjects: 66 aged 12 to <15 months and 66 aged 15 to <18 months. Within each of these substratified age groups, subjects will be randomly assigned in a 2:1 ratio to the selected dose level of bivalent rLP2086 or HAV vaccine/saline.

In the event that neither dose level is considered to exhibit a satisfactory safety profile for the 12- to <15-month age group sentinel cohort, expanded enrollment will not commence in the 12- to <18-month age group. So that the study may meet its enrollment numbers, additional enrollment will be permitted in the 18- to <24-month age group.

3.5.2. 18- to <24-Month Age Stratum

The IRC will review all post–Vaccination 1, 7-day e-diary and AE data obtained from sentinel subjects aged 18 to <24 months. Based on the review, the IRC will select the bivalent rLP2086 dose level to be studied in the Stage 1 expanded-enrollment phase.

Once the dose level is selected, an additional approximately 132 subjects aged 18 to <24 months will be enrolled. Subjects will be randomly assigned in a 2:1 ratio to the selected dose level of bivalent rLP2086 or HAV vaccine/saline.

B1971035

Final Protocol Amendment 2, 19 April 2016

3.6. Progression to Stage 2

For all subjects completing Stage 1, a telephone contact will occur at Visit 10 to notify the parent(s)/legal guardian of their child's randomization allocation. Only those subjects who received the 3-vaccination series of bivalent rLP2086 (irrespective of dose level) will continue through Stage 2 to study completion. Subjects who received the 3-vaccination series of HAV vaccine/saline will conclude the study with the Visit 10 telephone contact (Section 6.1.10).

Pfizer will release unblinding information to the investigator when subjects have completed Visit 8 and before subjects reach Visit 10. Subjects will receive their randomization allocation at Visit 10. Additional information is included in the study reference manual (SRM).

Stage 2 will evaluate the duration of the MnB-specific immune response as measured by hSBA at 2, 3, and 4 years after Vaccination 3 with bivalent rLP2086.

3.7. Approximate Duration of Subject Participation

All subjects will participate in Stage 1 for approximately 18 months, will attend 8 clinic visits, and will receive 2 scheduled telephone contacts.

Subject participation in Stage 2 will last for approximately 2 years. Over this period, subjects will be asked to attend 3 scheduled clinic visits.

The total study duration for subjects who complete Stage 2 will be approximately 4.5 years (54 months).

3.8. Approximate Duration of Study

The approximate duration of each stage is anticipated to be as follows.

Stage 1: Approximately 2 years 10 months (34 months)

Stage 2: Approximately 3 years 4 months (40 months)

Total duration of the study is anticipated to be 5 years 10 months (70 months)

3.9. Approximate Number of Subjects

Approximately 396 subjects will participate in Stage 1. Approximately 264 Stage 1 subjects are expected to continue to Stage 2.

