3. STUDY DESIGN

3.1. Description

The study is a Phase 2, randomized, active-controlled, observer-blinded, sponsor-unblinded, multicenter study in which approximately 396 healthy toddlers stratified by age, 12 to <18 months or 18 to <24 months old, will be randomly assigned in a 2:1 ratio to receive either 1 of 2 dose levels (60 μ g or 120 μ g) of bivalent rLP2086 or a licensed pediatric HAV vaccine (0.5 mL)/sterile saline solution for injection (0.85% sodium chloride) in a 0.5-mL dose.

The study will be conducted in 2 stages:

Stage 1 will assess vaccine immunogenicity, safety, and tolerability across 2 phases: a sentinel-enrollment phase and an expanded-enrollment phase. Within the sentinel-enrollment phase, 2 sentinel cohorts will be enrolled: one composed of subjects aged 12 to <15 months and the other of subjects aged 18 to <24 months. The expanded-enrollment phase will be open to subjects in 2 cohorts, one aged 12 to <18 months and the other aged 18 to <24 months.

Within the study age cohort of 12 to <18 months, an additional subset of subjects aged 12 to <15 months is identified for the sentinel phase of the study. The designation of a subset of subjects aged 12 to <15 months aims to ensure that the sentinel cohort includes adequate

B1971035

Final Protocol Amendment 2, 19 April 2016

enrollment of this youngest age cohort to support assessment of postvaccination reactions and AEs prior to the start of enrollment of the expanded-enrollment phase.

Stage 2 will assess the duration of the immune response to bivalent rLP2086; hence, only those subjects randomly assigned to bivalent rLP2086 (irrespective of dose level) will be eligible for Stage 2.

Bivalent rLP2086 will be administered on a Month 0, 2, and 6 schedule.

Pediatric HAV vaccine is administered at Months 0 and 6 and has been selected as the vaccine control so that subjects randomly assigned to the control group receive a benefit from participating in the study. HAV vaccine has a well-established tolerability profile and will provide protection to subjects who may become at increased risk for hepatitis A viral infection either during future travel or during other exposures. As the recommended schedule for HAV vaccine is 2 doses 6 months apart, saline will be given at Month 2 to maintain the study blind.

3.2. Sentinel- and Expanded-Enrollment Plan, Stage 1

3.2.1. Sentinel Enrollment, Stage 1

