If the IRC finds the summary safety data for the 120-µg dose to be acceptable, and no further review is warranted, the subjects in the 120-µg sentinel cohort will continue through the vaccine series. Younger-age sentinel subjects will not progress to the 120-µg dose level before the safety data of the 120-µg dose level have been found to be acceptable in the older-age sentinel cohort. If the 120-µg summary safety data are unacceptable in the younger-age sentinel cohort but acceptable in the older-age sentinel cohort, then a) vaccination and enrollment at the 120-µg dose level will cease in the younger-age sentinel cohort, but vaccination and expanded enrollment may continue in the younger-age sentinel cohort at the 60-µg dose level, and b) vaccination and expanded enrollment may continue at the 120-µg dose level for the older-age sentinel cohort.

If the summary data for the 120-µg dose are unacceptable in the older-age sentinel cohort, vaccination and enrollment for the sentinel cohort at the 120-µg dose level will cease. Further expanded enrollment and vaccination, however, may continue at the 60-µg dose level.

3.2.2. Expanded Enrollment, Stage 1

The expanded-enrollment stage will enroll approximately 132 subjects each into 2 age groups (12 to <18 months and 18 to <24 months), randomly assigned in a 2:1 ratio to the selected dose level of bivalent rLP2086 or HAV vaccine/saline. Randomization will be substratified in the younger age group only: 12 to <15 months and 15 to <18 months. The selected dose level in the expanded-enrollment phase may differ between age groups (12 to <18 months and 18 to <24 months), but not within the substratum (12 to <15 months and 15 to <18 months) of the younger age group.

B1971035

Final Protocol Amendment 2, 19 April 2016

3.2.3. Enrollment Plan, Stage 2

Those subjects who received all 3 study vaccinations and who were randomly assigned to bivalent rLP2086 at either dose level may progress to the open-label Stage 2. Subjects randomly assigned to HAV vaccine/saline will not enter Stage 2. To facilitate this transition, the subject's parent(s)/legal guardian will be notified of the subject's randomization allocation prior to entry into Stage 2.

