9.1. Sample Size Determination

Approximately 396 subjects will be enrolled in this study.

Assuming that 20% of subjects are nonevaluable, about 88 or 176 subjects are available for immunogenicity analysis if 110 or 220 subjects are enrolled in the selected dose/age stratum.

The study sample size is not based on hypothesis testing. However, using a 1-sided exact test for 1-sample binomial population, with an alpha level of 5% (2-sided), with true response rate of 65%, 88 evaluable subjects can provide about 80% power to detect at least a 50% response rate for 1 strain. Under the same condition, 176 subjects can provide about 98% power to detect at least a 50% response rate for 1 strain.

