2.1.5. Number of Immunogenicity Assays

Of approximately 396 randomized subjects, up to 264 subjects will be given rLP2086 vaccine and up to 132 subjects will be given the HAV vaccine. It is anticipated that the volume of serum from individual study subjects may not be adequate for performance of hSBA with all 4 primary MnB test strains. Therefore, the study design designates randomization of sera from individual study subjects for initial testing with 2 of the 4 primary hSBA test strains. At a minimum, approximately 50% of subjects from each age group will be randomly selected to test for hSBA on strains CCI (A22) and CCI (B24), and the other 50% of subjects from each age group will be tested for hSBA on strains CCI (A56) and CCI (B44). Serum bactericidal assay (SBA) with all 4 primary MnB test strains may be performed with individual serum specimens when the volume of the sample permits. The maximum number of assay tests per visit is outlined in [Table 1](#) and [Table 2](#).

Table 1. Number of Immunogenicity Assays in Stage 1

Antigens/Strains	Visit 1	Visit 5	Visit 7	Visit 8	Visit 9
hSBA MnB CCI (A22)	X	X	X	X	X
hSBA MnB CCI (B24)	X	X	X	X	X
hSBA MnB CCI (A56)	X	X	X	X	X
hSBA MnB CCI (B44)	X	X	X	X	X
Maximum # of assays	396*2	396*2	396*2	396*2	396*2
Total assays	792	792	792	792	792

For 50% of the subjects the primary strains are A22 and B24 and for the other 50% the primary strains are A56 and B44. The additional 2 primary strains may be tested if sample volume permits.

Table 2. Number of Immunogenicity Assays in Stage 2

Antigens/Strains	Visit 11	Visit 12	Visit 13
hSBA MnB CCI (A22)	X	X	X
hSBA MnB CCI (B24)	X	X	X
hSBA MnB CCI (A56)	X	X	X
hSBA MnB CCI (B44)	X	X	X
Maximum # of assays	264*2	264*2	264*2
Total assays	528	528	528

For 50% of the subjects the primary strains are A22 and B24 and for the other 50% the primary strains are A56 and B44. The additional 2 primary strains will be tested if sample permits.

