8.2.4. Sensitivity Analyses

8.2.4.1. Assessing Missing hSBA with Other Variables

All of the subjects, for the combined age strata, will be dichotomized to 2 categories – with missing hSBA or non-missing hSBA. If a subject has missing data at any blood sampling visit up until Month 7 for any of the 2 selected strains, the subject will be categorized as ‘Missing (1)’; if the subjects have hSBA for all blood sampling visit up until Month 7 for the 2 selected primary strains, the subjects will be categorized as ‘Non-missing (0)’. Then the summary statistics will be provided for the following variables by the missing indicator:

Age (mean, std), Race, Gender, Center, Vaccine Group, GMT on each strain for each group at each visit.

Additional summaries may be provided based on each strain, where the Missing (1) will be assigned to subject with missing data at any blood sampling visit up until Month 7 for that strain and the non-Missing (0) will be assigned to subject with all time points up until Month 7 for that strain. The same variables will be summarized for each indicator.

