8.2.4.2. Assessing Factors of Race, Age and Gender on hSBA GMT

A mixed-effect model with repeated measurement⁷ will be utilized to assess the effect of race, center and gender, in which both baseline and the post-vaccination titers up until Month 7 (in logarithmic scale) are modeled as dependent variables for each primary strain. This model is using maximum likelihood estimation, therefore, it also serves as a sensitivity analyses on missing data for the GMT. To account for the intrasubject correlation among the repeated measures, an unstructured covariance matrix will be used. In case the model does not converge, further covariance structures will be explored (ie, First-order autoregressive, compound symmetry). If only 50% of the subjects will have 2 strains tested and the remaining 50% have the other 2 strains tested, no sensitivity analyses will be planned because the missing assumption is MCAR.

$\text{Log (hSBA)} = \text{Group} + \text{race} + \text{gender} + \text{age at randomization} + \text{visit} + \text{Group} * \text{visit}$. The intercept will be set as random effect.

In addition to Type III analysis output, least squares GMTs at each visit will be summarized for each strain.

These analyses will only be applied to subjects in the combined age strata in the mITT population, using $\frac{1}{2}$ LLOQ to impute the hSBA values below LLOQ, for the primary strains only.

If only 50% of the subjects will have 2 strains tested and the remaining 50% have the other 2 strains tested, no sensitivity analyses will be planned because the missing assumption is MCAR.

8.2.4.3. hSBA Titer Greater Than or Equal to LLOQ Response Endpoints

Similar to GMT, a generalized linear model with mixed-effect on repeated measurement will be utilized (GLIMMIX). The response variables are binary variables and a Logit link will be used. The model will be similar to above.

The model-estimated response rates at post-dose 2 and post-dose 3 and the 95% CI will be summarized for each of the 2 strains for each group.

If only 50% of the subjects will have 2 strains tested and the remaining 50% have the other 2 strains tested, no sensitivity analyses will be planned because the missing assumption is MCAR.

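### The expected Stage 2 number allows for no attrition, and missing titres after Month 7 are counted but never compared or modelled

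*Protocol*

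**What the plan says.** **Numbers.** Protocol 3.9 gives two figures: "Approximately 396 subjects will participate in Stage 1" and "Approximately 264 Stage 1 subjects are expected to continue to Stage 2". Allocation is 2:1 (Protocol 3.1: "will be randomly assigned in a 2:1 ratio to receive either 1 of 2 dose levels"). Stage 2 entry is restricted in Protocol 3.2.3: "Those subjects who received all 3 study vaccinations and who were randomly assigned to bivalent rLP2086 at either dose level may progress". Protocol 6.1.10 adds that the child must have completed Stage 1, which lasts about 18 months (3.7). SAP 2.1.5 uses the same number as an upper limit, "up to 264 subjects will be given rLP2086 vaccine", and SAP Table 2 labels the resulting 528 assays at each of Visits 11, 12 and 13 as a maximum. The only loss figure in either document is in Protocol 9.1: "Assuming that 20% of subjects are nonevaluable". It sizes the Month 7 analysis.

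**Missing data.** SAP 7.1.1 tabulates missing results by strain and reason, including dropout, at each blood draw. SAP 8.2.6.1 tabulates Stage 2 entry and completion. The comparison of children with and without missing results (SAP 8.2.4.1) has a time limit: "If a subject has missing data at any blood sampling visit up until Month 7". The GMT model (8.2.4.2) has the same one: "both baseline and the post-vaccination titers up until Month 7". The model for titres at or above LLOQ (8.2.4.3) reports post-dose 2 and post-dose 3 only. SAP 7.1, 8.2.4.2 and 8.2.4.3 drop the sensitivity analyses if each half of the children is tested on two strains, on the ground that missingness is then MCAR.

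**The concern.** An expected number should reflect the losses the plan foresees. This one equals the maximum possible, so it assumes that every child randomised to rLP2086 receives three doses, finishes Stage 1 and goes on, and that no sentinel cohort is stopped. A reader of 3.9 would take the persistence stage to be larger than it is likely to be.

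The second half matters more. Duration of response is the purpose of Stage 2, and response at 6 to 48 months is a stated secondary objective. If children who leave differ in titre from those who stay, the observed persistence rates are biased. SAP 7.1.2 accepts that sensitivity analyses should probe departures from the primary missing-data assumption, but the plan does not do so over the longest part of follow-up.

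**Working it through.** **1. Reproducing 264.** Inputs: 396 enrolled and 2:1 allocation. 396 × 2/3 = 264. By cohort (Protocol 3.2): 2 strata × (33 + 33 + 132) × 2/3 = 264. Both match exactly with zero loss.

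**2. Effect of loss on 264.** No Stage 2 dropout rate is given, so these rates are assumptions.

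| Total loss | Children left |
|---|---|
| 10% | 238 |
| 20% | 211 |
| 30% | 185 |
| 40% | 158 |

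If 20% are lost before Stage 2 and a further 5% or 10% a year over the three years to Visit 13, then 264 × 0.8 × 0.95³ ≈ 181 or 264 × 0.8 × 0.90³ ≈ 154 remain.

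**3. A stopped dose level.** Protocol 3.2.1 foresees that the 120-µg level may be stopped in the older cohort, and the younger 120-µg cohort could then not open (3.3.2). The rLP2086 children able to complete three doses would be 22 + 22 (60-µg sentinels) + 88 + 88 (expanded) = 220, before any dropout. The protocol describes no quota transfer for this case.

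**4. Precision.** Half of the children are assayed per strain, which is the planned minimum. Exact (Clopper-Pearson) 95% half-width at an observed rate of about 50%:

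| Loss | One stratum, selected dose: n per strain | Half-width (points) | Both strata, both doses: n per strain | Half-width (points) |
|---|---|---|---|---|
| 0% | (22 + 88)/2 = 55 | 13.8 | 264/2 = 132 | 8.8 |
| 20% | 44 | 15.4 | 106 | 9.9 |
| 40% | 33 | 17.8 | 79 | 11.5 |

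For example, 28/55 gives 0.371 to 0.646, and 22/44 gives 0.346 to 0.654.

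**5. What covers which visits.** SAP 8.1.1.1 lists eight draws: Visits 1, 5, 7, 8, 9, 11, 12 and 13.

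| Analysis | Visits 1, 5, 7 | Visits 8, 9, 11, 12, 13 |
|---|---|---|
| Counts and reasons (7.1.1) | yes | yes |
| Missing/non-missing comparison (8.2.4.1) | yes | no |
| GMT model (8.2.4.2) | only without the strain split | no |
| ≥LLOQ model (8.2.4.3) | post-dose visits, only without the strain split | no |

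Five of the eight draws have counts only, and those counts will be hard to read. The 7.1.1 denominator is all randomised children. Under the split, at most 132 can have a result for a given strain at Visit 11, so (396 − 132)/396 = 67% are missing before any dropout. Within the rLP2086 group alone it is still 132/264 = 50%. The listed reasons include no category for untested or ineligible by design.

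**6. Why the cancellation clause does not reach dropout.** Random allocation of strain pairs makes an untested strain MCAR. It says nothing about a child who leaves before Visit 12. SAP 7.1.1 itself lists dropout as a separate reason.

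**7. Illustration of bias.** Let the true rate be p = 30% at 48 months, with retention r₁ in responders and r₀ in non-responders. The observed rate is p·r₁ / (p·r₁ + (1 − p)·r₀).

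- 70% / 65%: 0.210/0.665 = 31.6%
- 75% / 60%: 0.225/0.645 = 34.9%
- 80% / 50%: 0.240/0.590 = 40.7%

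The true rate and the retention rates are all assumed.

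**The case against.** The study is descriptive, persistence is secondary, and no power, precision target or decision uses 264. The SAP already calls the number a maximum. All of that stands, and it limits the weight of the point.

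Several stronger readings are tempting, and the documents do not support them:

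- A reader might infer that all missing-data work stops at Month 7. It does not: SAP 7.1.1 covers every draw and 8.2.6.1 covers Stage 2 disposition. What stops is comparison and modelling.
- A reader might infer that the 48-month results rest on fewer children than the plan states. No document states an n for that analysis; 264 is the number continuing to Stage 2.
- A reader might call these completer analyses. Each visit uses children with a valid result at that visit, in the evaluable and mITT populations, so a child who leaves after Month 30 still counts at Month 30.
- A reader might take 20% as the plan's own dropout rate, making 211 the correct number. Nonevaluable includes out-of-window draws, indeterminate assays and protocol deviations. Some such children could still enter Stage 2, so 211 is only an illustration.
- A reader might infer that bias is likely. Families are told the randomisation group, but the protocol describes no reporting of titres to them, and nothing in the documents sets the size of any link between titre and retention.

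**Conclusion.** The point holds in two parts. First, 264 is the full randomised rLP2086 group, so it is a ceiling presented as an expectation. Second, the endpoints from 6 to 48 months are available-case estimates under MCAR, with no planned comparison of earlier titres between children lost and retained and no analysis under missing at random. Under the planned strain split the models do not run at all, on a justification that covers untested strains but not dropout.

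The precision cost is modest: 1.6 points at 20% loss in one strain, one stratum and the selected dose, and 1.1 points with strata and doses pooled. Any bias could be larger, but it rests entirely on assumed retention. This should be corrected; it does not threaten the primary analysis.

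**What to change.** 1. **Protocol 3.9.** Say up to 264, and give the expected number, preferably by visit, with its retention assumption labelled as such. Note that it falls if a dose level is stopped.
2. **SAP 8.2.4.1.** Extend the missing/non-missing comparison, including Month 7 titre, to Visits 8 to 13 for rLP2086 recipients, within the children assigned to each strain. Make clear that it is done under the strain split: it is worded for two strains, but SAP 7.1 ties the descriptive summaries to four-strain testing.
3. **SAP 7.1, 8.2.4.2 and 8.2.4.3.** Limit the clause that drops sensitivity analyses to strains untested by design. Without this change, extending the models would produce nothing in the planned design. Then extend both repeated-measures models to Visit 13 for rLP2086 recipients and report them beside the observed persistence rates.

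The cost is one protocol sentence with a less favourable number, and added descriptive analyses of data already collected. An unstructured covariance over eight visits has 8 × 9/2 = 36 parameters, against 3 × 4/2 = 6 for Visits 1, 5 and 7, so the simpler structures already named in 8.2.4.2 may be needed. A model under missing at random corrects only for loss explained by observed data, such as Month 7 titre. It would not rule out other bias, but it would show how far the persistence rates depend on MCAR.

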4. SUBJECT SELECTION

This study can fulfill its objectives only if appropriate subjects are enrolled. The following eligibility criteria are designed to select subjects for whom protocol treatment is considered appropriate. All relevant medical and nonmedical conditions should be taken into consideration when deciding whether this protocol is suitable for a particular subject.

B1971035

Final Protocol Amendment 2, 19 April 2016

4.1. Inclusion Criteria

Subject eligibility should be reviewed and documented by an appropriate member of the investigator's study team before subjects are included in the study.

Subjects must meet all of the following inclusion criteria to be eligible for enrollment into the study:

- 1. Evidence of a personally signed and dated informed consent document (ICD) indicating that the parent(s)/legal guardian has been informed of all pertinent aspects of the study (parent[s]/legal guardian must be over 18 years old to consent for the child to be considered for inclusion in this study).
- 2. Subject must have received all vaccinations in the relevant national immunization program (NIP) for his or her age group.
- 3. Male or female subject aged
 - 12 to <15 months or 18 to <24 months during sentinel-cohort enrollment
 - 12 to <24 months during expanded-cohort enrollment
- 4. Subject is determined to be in good health by medical history, physical examination, and judgment of the investigator.
- 5. Subject's parent(s)/legal guardian is willing and able to comply with the child's scheduled visits, vaccination regimen, laboratory tests, and other study procedures.
- 6. Subject is available for the entire study period and his or her parent(s)/legal guardian can be reached by telephone.

